10.4 Interim Analyses, Missing Data and Stopping Rules

A planned interim analysis will be performed upon enrolling 12 evaluable subjects. Using a Fleming 2-stage design with a target accrual goal of 25 subjects, our null hypothesis is that the response rate is less than or equal to 0.400 versus the alternative that it is greater. Success for this study will be a response rate of at least 67% MRD negativity (< 0.01%). At the first stage we have 12 evaluable subjects and the cumulative number of successes, R , will be compared to the acceptance value and rejection value numbers for that stage. If $R \leq 4$, the study committee will reevaluate the study and determine if changes to the protocol design are necessary. If $R \geq 10$, then there is a very high chance of success. Similarly, after 25 evaluable subjects are recruited, if $R < 15$ we would not have met our 60% threshold. The type I error rate would be 0.0333. The power, calculated at a response rate of 0.670, is 0.8071. The calculation is done using PASS 15.

Missing Data: The dropout pattern will be plotted and summarized. Subjects who dropout before the first cycle of blinatumomab is completed will not have an MRD assessment. Subjects that are not MRD negative ($\geq 0.01\%$) at the end of the first cycle, proceed to a second cycle of blinatumomab, but dropout before the second cycle is completed will not have a final MRD assessment. Our primary outcome is the number of subjects who can achieve FC-MRD negativity (< 0.01%) after one or two cycles of blinatumomab. Hence the primary assessment is the proportion of subjects achieving FC-MRD negativity and completing these treatments.

However, secondary outcomes will include:

- The proportion of subjects achieving FC-MRD negativity (< 0.01%) after completing the first cycle of blinatumomab.
- The proportion of subjects achieving HTS-MRD negativity (MRD undetectable) after completing the first cycle of blinatumomab.
- The proportion of subjects achieving FC-MRD negativity (< 0.01%) out of all subjects recruited.
- The proportion of subjects achieving HTS-MRD negativity (MRD undetectable) out of all subjects recruited.

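### The Fleming two-stage error rates in section 10.4 do not follow from the printed limits, and neither stage-1 limit carries a stated decision

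*Combined protocol and SAP*

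**What the plan says.** Section 10.4 sets up the efficacy rule as follows: "Using a Fleming 2-stage design with a target accrual goal of 25 subjects". The hypothesis is one-sided: "our null hypothesis is that the response rate is less than or equal to 0.400 versus the alternative that it is greater". The first look is fixed at 12: "A planned interim analysis will be performed upon enrolling 12 evaluable subjects". The number of successes R "will be compared to the acceptance value and rejection value numbers for that stage".

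Two stage-1 limits follow. If R is 4 or fewer, "the study committee will reevaluate the study and determine if changes to the protocol design are necessary". If R is 10 or more, "then there is a very high chance of success". Fewer than 15 of 25 at the end counts as missing the threshold. The section then gives the operating characteristics: "The type I error rate would be 0.0333" and "The power, calculated at a response rate of 0.670, is 0.8071".

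No other section supplies a decision at the first stage. Section 10.2 lets accrual run on and mentions no interim stop for response. Section 10.7.2 plans a proportion with a 95% confidence interval. Section 11.1.4 gives the DSMC a general power to recommend continuing, suspending or ending the study, without tying it to the stage-1 count. By contrast, the toxic-death rule in section 10.4 goes to both the study committee and the DSMC and names termination as a possible outcome.

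**The concern.** In a Fleming design the stage-1 limits are terminal: at the lower one the null hypothesis is accepted, at the upper one it is rejected. The quoted error rates are calculated on that basis. Here the limits bear the names of acceptance and rejection values, but the actions attached to them are a committee discussion and a comment. A reader cannot tell whether 4 of 12 ends the trial, whether 10 of 12 establishes success, or which subjects make up the final 25 if the design is altered in between.

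Two things are at stake. First, whether the quoted type I error and power describe the printed rule under any reading. Second, whether a redesign made after seeing a poor first stage could feed the first 12 subjects into the final test with no valid error rate behind it.

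**Working it through.** **Inputs (all from section 10.4).** Null rate 0.40, alternative 0.67, n1 = 12, final N = 25 (so n2 = 13), lower limit 4, upper limit 10, final rejection at R ≥ 15. Quoted type I error 0.0333, quoted power 0.8071.

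**Formula.** With lower limit a and upper limit r, both binding:

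P(reject) = P(R1 ≥ r) + Σ over a < x < r of P(R1 = x) × P(Bin(13, p) ≥ 15 − x).

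**Printed limits, binding (a = 4, r = 10).**
- At 0.40, the terms for x = 5 to 9 are 0.0018, 0.0057, 0.0099, 0.0096 and 0.0053, total 0.0322. Adding P(R1 ≥ 10) = 0.0028 gives **0.0350**.
- At 0.67, the same terms are 0.0151, 0.0607, 0.1441, 0.2148 and 0.2081, total 0.6428. Adding P(R1 ≥ 10) = 0.1876 gives **0.8303**.

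**Printed limits, ignored (all 25 treated, R ≥ 15).** P(Bin(25, 0.40) ≥ 15) = **0.0344** and P(Bin(25, 0.67) ≥ 15) = **0.8314**.

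**Acceptance number 5, binding (a = 5, r = 10).** The x = 5 term drops out.
- At 0.40: 0.03502 − 0.00177 = 0.03325, which is the quoted **0.0333**.
- At 0.67: 0.8303 − 0.0151 = **0.8152**. This is nearer to the quoted 0.8071 but not equal to it; at a rate of 0.667 the same rule gives 0.8066.

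Fleming's boundary formula at one-sided 0.05 points the same way. With z = 1.645, p_A = (√(25 × 0.40) + √0.60 × z)² / (25 + z²) = 0.710, and the lower limit is 12 p_A − z√(25 p_A(1 − p_A)) = 4.79, which rounds to 5. The upper limits are 8.83 and 14.03; each is rounded and one added, giving 10 and 15 as printed.

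| Rule | Type I error at 0.40 | Power at 0.67 |
|---|---|---|
| Quoted in 10.4 | 0.0333 | 0.8071 |
| 4 / 10 / 15, both binding | 0.0350 | 0.8303 |
| 4 / 10 / 15, only the lower limit ignored | 0.0353 | 0.8325 |
| 4 / 10 / 15, only the upper limit ignored | 0.0341 | 0.8292 |
| Both ignored, R ≥ 15 of 25 | 0.0344 | 0.8314 |
| 5 / 10 / 15, both binding | 0.0333 | 0.8152 |

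Reading success as 67% (17 of 25), which section 10.4 also mentions, does not recover the quoted pair: 0.0064 and 0.566 with binding limits, 0.0043 and 0.552 without.

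**The R ≤ 4 branch.** P(Bin(12, p) ≤ 4) is 0.438 at 0.40 and 0.018 at 0.67. If the trial then continues unchanged, the chance of reaching 15 of 25 is 0.0007 at 0.40, 0.045 at 0.60 and 0.12 at 0.67. The branch therefore adds 0.438 × 0.0007 = 0.0003 to the type I error. If the protocol is changed and the first 12 are kept, no single response rate governs the 25 and the choice to change depends on the data, so no error rate can be calculated from what the plan states.

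**The case against.** The strongest reply is that the limits are labelled as acceptance and rejection values, that a non-binding look is legitimate, and that it costs almost nothing here. On size this is right: ignoring both limits moves type I error from 0.0350 to 0.0344 and power from 0.8303 to 0.8314. Going on to 25 after a strong first stage also serves the interval-width goal in section 10.3.1. Any design change would need an IRB-approved amendment under section 12.8, and the DSMC reviews the study twice a year.

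A reader might infer four stronger conclusions that the documents do not support.

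- *That the missing decisions materially inflate type I error.* With an unchanged protocol they do not. The largest effect, from ignoring only the lower limit, is 0.0353 − 0.0350 = 0.0003.
- *That the missing decisions explain the wrong figures.* The quoted pair also fails with the limits fully binding. For type I error, the acceptance number of 4 rather than 5 is the likelier cause.
- *That the true type I error is about 0.05.* A restart with a fresh cohort under the same rule would give 0.0350 + 0.438 × 0.0350 = 0.050, but section 10.4 describes no such restart.
- *That the optimistic remark at R ≥ 10 is wrong.* At exactly 10 of 12, the chance of reaching 15 is 0.65 at a true rate of 0.40, but P(R1 ≥ 10) is then only 0.003. At 0.67 the chance is 0.99.

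The reply leaves two things unanswered. The quoted figures match no reading of the printed limits. An approved amendment would also not settle whether the first 12 subjects count in the final test.

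**Conclusion.** The point holds in a limited form. The quoted 0.0333 and 0.8071 are not the operating characteristics of the printed rule, binding or not. The gaps are about 0.001 to 0.002 in type I error and 0.023 to 0.024 in power, and the true power is higher than stated, so the trial is not underpowered by this route. The match to an acceptance number of 5 is an inference from the arithmetic; the documents do not say which limits were entered in the software, and the quoted power is not reproduced exactly.

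The substantive gap is the unstated decision at R ≤ 4. It matters only if the protocol is changed there and the first 12 subjects are reused, but the branch that allows this has a 44% chance when the null rate is true.

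The figures assume 25 evaluable subjects, independent responses at a common rate, and 15 of 25 as the final cut-off. Section 10.2 states a different accrual rule (25 MRD-negative subjects or 35 recruited); the calculation does not cover that rule.

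**What to change.** Choose one of two wordings for section 10.4.

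1. Declare the stage-1 look advisory, with no formal acceptance or rejection, and quote the single-stage figures for R ≥ 15 of 25: type I error 0.0344, power 0.831. This has no operational cost.
2. State the decision at each limit: the null is accepted at R ≤ 4 and rejected at R ≥ 10, saying in each case whether enrolment continues. Quote the figures for the limits as printed: 0.0350 and 0.830. If the intended acceptance number was 5, print 5 and quote 0.0333 and 0.815. The cost is discretion given up after a poor first stage.

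Under either wording, add that subjects treated before a design change are not pooled with later subjects in the primary test unless the error rates are recalculated for the design actually followed. All of this is protocol and SAP text, and it should be settled before the 12-subject look so that the rule is not chosen with the data in view.

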10.5 Analyses Plans

The primary objective is to determine the efficacy of giving blinatumomab immediately prior to HCT as “bridging therapy” to eliminate MRD (as measured by flow cytometry) in children, adolescents and young adults with relapse, refractory or persistent MRD B-ALL.

10.6 Analysis Population

This will include all subjects who have completed at least one course of blinatumomab and for whom there is an assessment of MRD. **This will be the primary efficacy analysis group since we will assess the ability to proceed for HCT.**

All Enrolled Cases: This will include all subjects enrolled. If any dropout or die they will be included in the MRD positive group. This is a less enriched group and will be mainly used for assessment of feasibility of the treatment.

Per Protocol Cases: The per-protocol population will be defined as the subset of the observed cases (OC) who completed all treatments and who did not have any major protocol violations (such as lack of compliance to the study medication schedule). The definitions of these protocol violations will be finalized before the database closure and will be documented in the analysis plan. The analysis of this group will be exploratory.

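### The primary efficacy set drops treated subjects who fail before the first MRD result, and the plan does not fix who is evaluable, what 25 counts, or whether 60% or 67% is success

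*Combined protocol and SAP*

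**What the plan says.** **Who is analysed.** Section 10.6 describes the primary efficacy group: "This will include all subjects who have completed at least one course of blinatumomab and for whom there is an assessment of MRD". The reason it gives is that ability to go on to HCT will be assessed. Section 10.4 adds: "Subjects who dropout before the first cycle of blinatumomab is completed will not have an MRD assessment". Subjects who are still positive after Cycle 1 and then "dropout before the second cycle is completed will not have a final MRD assessment". It concludes: "Hence the primary assessment is the proportion of subjects achieving FC-MRD negativity and completing these treatments". Section 9.1.1 has its own definition of evaluable for response. It needs at least one cycle and a disease re-evaluation, but a note adds subjects who progress before the end of Cycle 1.

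**What 25 means.**
- The protocol summary (number of subjects), 3.2 and 10.2 attach 25 evaluable to subjects who become flow MRD negative or can proceed to HCT. Section 10.2 stops accrual at 25 such subjects or at 35 recruited.
- Sections 10.3.1 and 10.4 use 25 as the number assessed. The final stage in 10.4 begins: "Similarly, after 25 evaluable subjects are recruited".
- Section 5.5.5 presents 35 enrolled as an allowance for withdrawals that leaves 25 evaluable.

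**What counts as success.** Section 10.4 states: "Success for this study will be a response rate of at least 67% MRD negativity". It then says that with fewer than 15 responses in 25 "we would not have met our 60% threshold".

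**What covers the early failures.** The All Enrolled set in 10.6 codes dropouts and deaths as MRD positive but is mainly for feasibility. Section 10.4 lists, as a secondary outcome, the proportion negative "out of all subjects recruited".

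**The concern.** The trial has one arm and is judged on one proportion, so the denominator largely determines the answer. A subject who progresses or dies in Cycle 1 has plainly not cleared MRD and has not gone on to HCT, yet is absent from the primary proportion. The reason 10.6 gives for its set would argue for counting that subject. Because 9.1.1 and 10.6 disagree on early progressors and 10.4 says only evaluable, two analysts could apply the 12/25 rule to different subjects and both be following the plan. They could also reach opposite conclusions from the same 15 or 16 responses in 25, depending on whether they use 60% or 67%.

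**Working it through.** **1. Classify the subjects.**

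| Subject | 10.6 primary set | 9.1.1 evaluable | All Enrolled |
|---|---|---|---|
| Progresses in Cycle 1 | out | in | in; positive if a dropout or death |
| Dies or stops in Cycle 1 without documented progression | out | out | in, positive |
| Positive after Cycle 1, drops out in Cycle 2 | in by definition, but 10.4 gives no final assessment | in | in, positive |

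The third subject's only result is positive and treatment was not completed, so no reading makes this a success. Only inclusion in the denominator is open.

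**2. Identify what 25 is.** Exact (Clopper-Pearson) intervals:
- 20/25 gives (0.593, 0.932); 10.3.1 prints (0.59, 0.93).
- 10/25 gives (0.211, 0.613); 10.3.1 prints (0.21, 0.61).
- So 25 is a denominator in 10.3.1.
- The 35-subject interval, 0.67 (0.47, 0.83), is matched by 20/30, which gives (0.472, 0.827). With n = 35 the nearest are 23/35 (0.478, 0.809) and 24/35 (0.507, 0.831).

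Under 10.2, accrual stops at 25 negatives or 35 subjects. If every subject is assessed, mean accrual is the sum over n = 0 to 34 of P(Bin(n, p) ≤ 24). That is 31.1 at p = 0.80 and 34.3 at p = 0.67. The chance of 25 negatives within 35, P(Bin(35, p) ≥ 25), is 0.925 and 0.360. The trial would usually run past 25 subjects, where 10.4 has no boundary.

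**3. Reproduce the 10.4 rule.** Inputs from 10.4: 12 then 25 subjects, stage 1 limits 4 and 10, final cut 15, null 0.40, alternative 0.67. I score 10 or more of 12 as a pass and 4 or fewer as not passing. Both are readings, since 10.4 speaks only of a very high chance of success and of committee re-evaluation. With X1 ~ Bin(12, p) and X2 ~ Bin(13, p):

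P(pass) = P(X1 ≥ 10) + Σ(x = 5 to 9) P(X1 = x) · P(X2 ≥ 15 − x)

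- p = 0.40: 0.0028 + 0.0322 = 0.0350 (stated 0.0333).
- p = 0.67: 0.1876 + 0.6428 = 0.830 (stated 0.8071).
- With a stage 1 limit of 5 instead of 4: 0.0333 and 0.815.

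The printed limit reproduces neither stated figure. A limit of 5 reproduces alpha. Neither limit gives 0.8071.

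**4. Compare the two criteria.** 0.60 × 25 = 15. 0.67 × 25 = 16.75, so 67% needs 17. Observed 15/25 (60%) and 16/25 (64%) pass one and fail the other. Replacing 15 by 17 in the formula gives alpha 0.006 and power 0.566, so the stated power is close only to the 15-of-25 rule.

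**5. Illustrate the exclusion.** Let d be the share of treated subjects with no assessment. The documents give no value; 5, 10 and 20% are assumptions. Assume also that all of these subjects are failures and that 0.40 is the treated-population rate. The rate among completers is then 0.40/(1 − d):

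| d | Completer rate | P(pass), 15 of 25 |
|---|---|---|
| 0 | 0.400 | 0.035 |
| 5% | 0.421 | 0.055 |
| 10% | 0.444 | 0.088 |
| 20% | 0.500 | 0.213 |

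Put as counts, a just-passing 15/25 is 15/28 = 53.6% of treated subjects if three were excluded, and 15/30 = 50.0% if five were.

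**The case against.** The plan is not silent on the excluded subjects. The All Enrolled analysis codes dropouts and deaths as positive, the all-recruited proportion is listed, adverse-event dropouts are reported as a safety outcome, and toxic deaths are monitored over all patients treated. A completer rate is also a legitimate quantity. For it the binomial error rates hold, and 10.4 does not say that 0.40 refers to treated subjects. A toxicity stop need not be an MRD failure: Section 7.0 allows a patient permanently discontinued for toxicity to go on to HCT. Finally, a cut at 60% between a null of 0.40 and an alternative of 0.67 is coherent, and 17 of 25 appears nowhere in the plan.

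Much of this stands. The supplementary analyses make the early failures visible, and the bias is clear only for progression and death. But none of those analyses is the primary efficacy estimate, and none settles who is evaluable in 10.4, what 25 counts, or which percentage decides.

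Three stronger readings are tempting and not supported:
- That the go/no-go rule certainly ignores early failures. Section 10.4 never names the 10.6 set, and under 9.1.1 early progressors would count.
- That Cycle 2 dropouts could be scored as successes. They could not.
- That alpha and power should simply be restated as 0.035 and 0.83. A stage 1 limit of 5 returns the stated alpha, so the printed limit may be the error.

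**Conclusion.** The point holds as a conflict of definitions together with a primary proportion that omits early failures. The text conflicts are firm. The upward bias for the treated population is clear for progression and death; for toxicity stops it depends on MRD status that the plan does not observe. Its size cannot be fixed from the documents. The rise from 0.035 to between 0.055 and 0.213 is an illustration resting on the assumed non-completion rates, on all non-completers being failures, and on 0.40 being a treated-population rate. If 0.40 is meant for completers, the rule's type I error does not change. This should be fixed before the interim look at 12 subjects, because the decision rule cannot be applied unambiguously as written.

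**What to change.** - Use one definition in 9.1.1, 10.4 and 10.6: every subject who received any blinatumomab, with no post-treatment flow MRD result counted as not MRD negative.
- State in advance how a marrow taken after early discontinuation counts, and that subjects positive after Cycle 1 who drop out in Cycle 2 stay in as not negative.
- Apply the 12/25 rule to the first 12 and first 25 such subjects. Keep the present 10.6 set as a sensitivity analysis.
- State the HCT/Part 2 responder target in the summary, 3.2 and 10.2 separately from the efficacy denominator, and align 5.5.5. Report subjects 26 to 35 descriptively or against a pre-set boundary.
- Name one success criterion, and say whether 0.40 and 0.67 refer to treated subjects or completers.
- Reconcile the 10.4 limits, alpha and power with the software output, and correct the n behind 0.67 (0.47, 0.83).

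The cost is an amendment to the primary population. It needs no enrolment above 35 and reuses the failure coding of the All Enrolled set. There may be a power cost. If 0.67 is a completer rate, the treated rate is 0.67 × (1 − d), that is 0.6365, 0.603 and 0.536 at 5, 10 and 20% non-completion. Power at 15 of 25 then falls from 0.83 to 0.72, 0.60 and 0.33. If 0.67 is the target for treated subjects, power under the printed limits stays 0.83.

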10.7 Primary Analysis (or Analysis of Primary Endpoints)

10.7.1 Endpoints to be Collected

- FC-MRD: minimal residual disease measured by flow cytometry at the end of each cycle of blinatumomab.
- HTS-MRD: minimal residual disease measured by high throughput sequencing at the end of each cycle of blinatumomab.
- Severe Adverse Events: Grade 3 and 4 adverse events attributed to blinatumomab.
- Toxic death rate: deaths attributed to blinatumomab treatment prior to HCT.

10.7.2 Primary Endpoint

The proportion of subjects who are FC-MRD negative (< 0.01%) will be summarized with 95% CI.

10.7.3 Secondary Analysis (or Analysis of Secondary Endpoints)

10.7.3.1 Secondary Endpoints

- The proportion who are HTS-MRD negative (MRD undetectable) will be summarized with 95% CI.

10.7.4 Other Analyses/Assessments

We will summarize by and compare the subgroups of those who are MRD negative by Flow Cytometry AND HTS will be compared to those subjects who are MRD negative by only Flow Cytometry (HTS MRD positive) by demographics and by # of cycles (incomplete, 1 or 2). For comparison of continuous data, we will use a t-test or non-parametric Mann Whitney test, if needed due to distribution. For categorical data we will use a Fisher exact test.

10.7.5 Evaluation of Safety

Safety population: The safety population will consist of all subjects who have received any amount of blinatumomab, whether withdrawn prematurely or not.

All information on AEs and SAEs will be listed by patient and will be summarized. The SAE report will include event term(s), serious criteria, and the sponsor-investigator's or sub-investigator's determination of both the intensity of the event(s) and the relationship of the event(s) to study drug administration. Intensity for each SAE, including any lab abnormalities, will be determined by using the NCI CTCAE (Version 5.0) as a guideline whenever possible.

Frequencies will be presented for the categorical variables (e.g., race) and descriptive statistics will be presented for continuous variables (e.g., weight, age).

10.7.6 Adverse Events of Special Interest (Immediately Reportable to the Sponsor)

Adverse events of special interest are required to be reported by the investigator to the Sponsor immediately (i.e., no more than 24 hours after learning of the event; see Section 8.4 for reporting instructions). Adverse events of special interest for this study are as follows: Cytokine Release Syndrome (CRS) and Neurological Adverse Events.

11.0 DATA AND SAFETY MONITORING PLAN (DSMP)

Please refer to the MCWCC DSMC Charter.

11.1 Data and Safety Management Overview

The Medical College of Wisconsin (MCW) Data Safety Monitoring Committee (DSMC) and the Children's Hospital of Wisconsin Institutional Review Board (CHW IRB) will approve protocol-specific DSM plans. A local, investigator-initiated trial will be required to be continuously monitored by the principal investigator of the study with (biannual, monthly) safety and progress reports submitted to the DSMC.

